#### **Trial Design**

This study will be carried out as a prospective, randomized, single-blinded clinical trial.

The intervention group will receive intraoperative laparoscopically assisted, surgeon-placed TAP blocks using 1mL/kg of 0.25% bupivacaine with epinephrine 1:200,000 combined with 16mg dexamethasone divided into 4 aliquots to be placed at two locations per side along the anterior axillary line between the

costal margin and the iliac crest. The control group will have TAP blocks with the same dose of bupivacaine without dexamethasone. The blocks will be performed at the conclusion of surgery. Postoperatively, all patients will be provided with patient-controlled analgesia (PCA) with institutional standardized orders.

Intravenous dexamethasone will not be given for prevention of postoperative nausea and vomiting (PONV); prophylaxis of postoperative nausea and vomiting will be at the discretion of the anesthesiologist, but can include any of ondansetron, haloperidol, or dimenhydrinate. If PONV occurs and is refractory to non-corticosteroid treatment, dexamethasone may be given for treatment but would result in exclusion from the trial. General anesthetic technique will be at the discretion of the anesthesiologist, but the following adjunct anesthetic drugs will not be permitted, due to independent effects on postoperative pain: dexmedetomidine, lidocaine, and ketamine. These adjuncts are occasionally used in anesthetic protocols, but their exclusion will not affect the quality of the anesthetic provided, and their use is not considered standard of care. All patients will be provided with a standardized hydromorphone-based patient-controlled analgesia (PCA) for a minimum of 48 hours postoperatively.

The primary outcome will be total opioid consumption, in hydromorphone equivalents, in the first 48 hours after surgery. Secondary outcomes will be length of stay in the post-anesthetic care unit (PACU), length of stay in hospital, and total opioids administered in the PACU.

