A computer-generated random number table will be used to randomize patients to receive either bupivacaine alone (n=60) or bupivacaine plus dexamethasone (n=60). Allocation will be performed in a 1:1 ratio. Group allocation will be concealed via a centralized third-party research assistant. Group allocation will be blinded to study participants, study investigators, post-anesthetic care unit (PACU) nursing staff, and surgical ward nursing staff. The attending surgeon and attending anesthesiologist on the day of surgery will not be blinded to the intervention, however, they will be asked to conceal the anesthetic modality from the PACU staff and ward nurses. The intervention will be charted in the Operating Room record, but not on the anesthetic record. PACU nurses commonly review the anesthetic record, whereby they would discover the intervention.

A blinded, centralized, third-party research assistant or study investigators will carry out data collection. Postoperative opioid consumption will be quantified through chart review as well as assessment of patient-controlled analgesia (PCA) usage at 24 and 48 hours following the operation. Recording the doses of opioids administered in the medication administration record (MAR) is standard practice by PACU nursing staff at the study institution. PCA pumps automatically document cumulative opioids administered and can easily be checked at the bedside, as well as being recorded in the MAR. Length of stay in hospital is readily available from the chart.

Followup for primary and secondary outcomes will be limited to 48 hours postoperatively, and assessment of infiltration sites for complications will be performed at 6 weeks postoperatively.

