#### Selection and withdrawal of subjects

We intend to enroll a sample size of 120 patients based on an alpha set at 0.05, power set at 0.08, and the effect size set at 0.8.

Inclusion criteria are: age > 18, ASA class I-III patients scheduled for elective or urgent inpatient laparoscopic/laparoscopic assisted colorectal surgery.

Exclusion criteria are: emergency surgery, open surgery, contraindications to laparoscopic surgery (ie. adhesions, inability to tolerate pneumoperitoneum), ASA class  $\geq 4$ , age < 18, pregnant or breastfeeding women, significant cardiorespiratory/hepatic/renal disease, allergy to any study drugs, inability to consent, inability to respond to pain assessments, inability to use the patient-controlled analgesia device (PCA), preoperative chronic opioid use.

Potential participants will be identified by their attending surgeon during their initial clinic surgical consultation. This typically occurs several weeks in advance of their scheduled surgical procedure. Information detailing the study, as well as contact information of the research team will be made available to patients at this time should they have any questions. After having had a chance to review the study information provided to them by their surgeon, prospective patients will be assessed by study staff (attending surgeon or designate such as a general surgery resident) and asked to sign a consent if they agree to participate and meet the inclusion criteria. The consent will be taken on the day of surgery.

Participants who are unable to personally provide informed consent will be excluded from the study. No third party will be allowed to consent on the participants behalf. Capacity will be assessed by the study staff or designate obtaining consent. All patients participating must be assessed to determine that they fully understand the protocol, risks, and benefits of participating in the study.

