Subjects will be free to withdraw voluntarily from the study at any point. The process for withdrawal can be initiated by the participant at any time by informing any of the study staff of the decision to withdraw. No explanation for withdrawal will be sought. If this occurs prior to randomization, no patient information will be collected for study purposes, and the patient will still be eligible to undergo surgery as planned without compromise to care. If withdrawal occurs during data collection, data collected on the subject will be destroyed, and they will continue receiving post-operative care as per standards. Either of the attending anesthesiologist or attending surgeon caring for the patient on the day of surgery has the ultimate discretion as to whether a patient is included or excluded from the study. If the attending surgeon or anesthesiologist deems the patient unfit to participate in the study, this will be communicated to the study coordinator, and the patient will be withdrawn. All adverse events and protocol deviations will be reported to the study coordinator, study investigators, and appropriate Research Ethics Board. Subjects who are withdrawn from the study due to the occurrence of an adverse event will be followed up by one of the study's physician investigators while in hospital. If the adverse event is believed to have been related to the study drug, a detailed note will be made in the patient's medical record and passed on to future care providers. Subjects withdrawn from the study due to an adverse event will not be replaced. Any adverse events will result in unblinding by notification of the principle investigator.

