#### **Statistics**

Primary Outcome:

Total opioid consumption at 24 and 48 hours will be gathered from the PCA record and Medication Administration Record (MAR). Intention to treat analysis will be performed. Parametric data will be analyzed with the students t-test for statistical significance.

Secondary Outcome: Opioid consumption in the PACU will be reported in hydromorphone equivalents and compared with chi square test. Length of stay in PACU and length of stay in hospital will be reported as a mean +/- standard deviation (SD), along with confidence intervals and compared with chi square test.

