#### **Quality Control and Quality Assurance Procedures**

Patients will be monitored intraoperatively by a qualified staff anesthesiologist. Following surgery, patients will be extubated fully awake in the operating room and transferred to the PACU with supplemental oxygen. In PACU patients will be monitored by dedicated nursing staff and will have access to nurse-administered analgesia. Standard antiemetics will be available as well, and dexamethasone can be given systemically as a rescue antiemetic. If this occurs, the patient will be excluded from the study. Following discharge from PACU, patients will be monitored on the ward by nursing staff and postoperative care will be administered as per usual protocol.

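### Day-of-surgery withdrawal by unblinded clinicians is not limited to the time before randomisation, which leaves the intention-to-treat commitment unprotected

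*Protocol*

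**What the plan says.** Four statements in the protocol bear on this point.

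- **Analysis (Statistics).** "Intention to treat analysis will be performed". No qualification follows.
- **Clinician withdrawal (Selection and withdrawal of subjects).** Either attending clinician caring for the patient on the day of surgery "has the ultimate discretion as to whether a patient is included or excluded from the study". The ground is that the clinician considers the patient not fit to take part. The consequence is that "this will be communicated to the study coordinator, and the patient will be withdrawn".
- **Blinding (Trial Design).** "The attending surgeon and attending anesthesiologist on the day of surgery will not be blinded to the intervention". They are asked only to keep the treatment from PACU and ward nurses.
- **Timing.** "The consent will be taken on the day of surgery" (Selection and withdrawal of subjects). The block is placed at the end of the operation (Trial Design; Treatment of subjects). The protocol does not say when randomisation takes place or when the two clinicians learn the arm.

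**The concern.** Intention to treat protects the comparison only if everyone randomised is followed and counted in the arm assigned. A rule that lets someone who knows the allocation take a patient out of the study works against this. If such removals relate to expected pain or opioid need, and do so differently in the two arms, the difference in 48-hour opioid use reflects who was kept as well as what was injected. Losing high-use patients from the dexamethasone arm would create or enlarge an apparent benefit; losing them from the control arm would hide one.

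A later analysis plan cannot fully repair this. It can say how withdrawn patients are to be analysed, but it cannot recover outcomes that were not collected because the patient had left the study.

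**Working it through.** **Step 1: can the rule operate after randomisation?** The protocol gives no figure to reproduce here, so the passages are set side by side.

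- In the same section, the text on participant-initiated withdrawal separates what happens before randomisation from what happens during data collection. The text on clinician withdrawal makes no such separation.
- Consent is taken on the day of surgery. If randomisation follows consent, as is usual but not stated, it cannot fall before that day. The clinicians' discretion is also placed on that day, so the two can overlap.
- The block comes at the end of surgery. The whole operation may therefore lie between allocation and study treatment. The exclusion criteria include open surgery and adhesions, which may first become apparent during the operation and may relate to later opioid need.
- The section also provides for subjects withdrawn because of an adverse event, and says that they are not replaced. Withdrawal after treatment is thus foreseen elsewhere in the same text.

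The wording therefore permits clinician withdrawal after randomisation. It does not say that this is intended.

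**Step 2: is the outcome kept?** No section says that a clinician-withdrawn patient's opioid total continues to be collected. The only data rule attached to withdrawal is "If withdrawal occurs during data collection, data collected on the subject will be destroyed", which stands in the text on participant-initiated withdrawal. The data would otherwise exist: Trial Design says that PCA pumps log cumulative doses and that opioid doses are entered in the medication administration record (MAR).

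**Step 3: how large could the effect be?** The 60 per arm and the 0.05 level are the protocol's; everything else is assumed. There is no true effect, the outcome is normal, the test is a two-sided t-test, and the k patients with the worst clinician-judged prognosis are removed from one arm only. Judgement correlates ρ with 48-hour opioid use. Each setting was simulated 20,000 times, with a simulation standard error near 5% of √(0.05 × 0.95 / 20,000) = 0.15 percentage points.

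| Removed from one arm | ρ = 0.3 | ρ = 0.5 | ρ = 0.7 |
|---|---|---|---|
| 0 of 60 | 4.9% | 4.7% | 4.8% |
| 3 of 60 (5%) | 5.6%, shift 0.03 SD | 6.3%, shift 0.05 SD | 7.4%, shift 0.08 SD |
| 6 of 60 (10%) | 6.0%, shift 0.06 SD | 8.6%, shift 0.10 SD | 12.2%, shift 0.13 SD |

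Percentages are type I error; the shift is the false difference in means.

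A closed form checks the shifts: shift ≈ ρ × m × k / (60 − k), where m is the mean of the top k/60 of a standard normal (about 2.06 for 5% and 1.755 for 10%).

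- k = 3: 0.3 × 2.06 × 3/57 = 0.033, and 0.7 × 2.06 × 3/57 = 0.076.
- k = 6: 0.3 × 1.755 × 6/54 = 0.059, and 0.7 × 1.755 × 6/54 = 0.137.

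These agree with the simulation (0.032, 0.075, 0.056 and 0.133). With ρ = 0 the formula gives a shift of zero.

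**The case against.** The strongest reply is that the rule is an entry check. Consent is taken the same day, and fitness to take part is naturally judged at that moment. The rule concerns participation and does not say who is analysed; the only statement on analysis is intention to treat, whose ordinary meaning already keeps randomised patients in. How withdrawn patients are handled in detail is commonly left to the analysis plan, which is not at hand.

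Much of this stands, and it rules out several stronger readings that a reader might infer.

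- *The protocol defines two analysis populations.* It does not. It has one analysis statement and one participation rule that can undercut it.
- *Clinicians may drop anyone they choose.* The text does give a ground, namely fitness to take part, although it does not define it.
- *Clinicians will know the arm and see the operation before deciding.* This is possible under the text but not described there.
- *Data of clinician-withdrawn patients are destroyed.* The destruction rule is not stated for them.
- *The trial's type I error is inflated by a known amount.* The protocol gives no withdrawal rate and no link between clinician judgement and outcome. Removal from one arm only is an unfavourable assumption.

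It might also be said that clearer conflicts with intention to treat exist. After rescue treatment for refractory nausea and vomiting, "dexamethasone may be given for treatment but would result in exclusion from the trial" (Trial Design), and Quality Control and Quality Assurance Procedures repeats that "If this occurs, the patient will be excluded from the study". Those, and the destruction of data when a participant withdraws, are separate routes. Closing them would not close this one.

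What remains is a stated rule of conduct without a cut-off. It can be followed to the letter and still remove a randomised patient and end outcome collection. That is more than a detail awaiting an analysis plan.

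**Conclusion.** The point holds as an unresolved conflict between the withdrawal rule and the intention-to-treat commitment. The rule allows removal after randomisation by a clinician who may know the arm, and the protocol does not secure that patient's 48-hour outcome. It does not show that such removals will occur or that they were intended.

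The size of any bias is unknown. Under the stated assumptions the false shift is 0.03–0.08 SD for 3 of 60 removed and 0.06–0.13 SD for 6 of 60. These figures show sensitivity to a scenario and do not estimate what this trial will suffer. If removals are unrelated to arm and prognosis, the cost is precision only. The correction is worth making because it is nearly free. If an entry check was meant, it only writes that down.

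**What to change.** Reconcile the withdrawal rule with the Statistics section by stating three things.

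1. Exclusion from the study by the attending surgeon or anesthesiologist applies only before randomisation.
2. After randomisation, a clinician's decision about care does not remove the patient from follow-up or from the intention-to-treat analysis. The 24- and 48-hour opioid totals and the lengths of stay are still taken from the PCA record, MAR and chart, unless the participant withdraws consent.
3. The number of such decisions and their reasons are reported by arm.

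Decisions about care stay with the clinicians, and the wording should not prescribe a treatment rule. It would also help to state when randomisation takes place and when the clinicians are told the arm.

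The cost is a few sentences in an amendment. No patients, visits or procedures are added, because the data come from records already kept. The one drawback is slight dilution of the effect, since some patients who did not receive the assigned block stay in the comparison.

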#### **Stopping Criteria**

Interim analysis will be performed after 50% enrolment. If either arm is found to be superior, the trial will be discontinued. If any adverse events are identified in either arm, a safety review will be performed. Should a significant safety concern be identified, the trial will be discontinued.

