#### Assessment of safety

Following surgery, adequacy of analgesia will be closely monitored, and inadequate analgesia will be treated as per standard protocol in the postanesthetic care unit (PACU). Physical examination of the TAP block injection sites will be performed daily and at the 6 week postoperative follow up visit. Diabetic patients will have blood glucose monitoring as per standard protocol, and all patients will have serial vital signs four times daily. Clinical assessment for severe postoperative nausea and vomiting (PONV) will be performed as per nursing protocol, and by the attending anesthesiologist on daily round. Any serious adverse events will be followed closely until resolution, with frequency of follow up to be determined by clinical judgement. Education to ward nurses will be provided on identification and reporting of adverse events. Adverse events will be recorded in the data collection tool. All serious adverse events will be reported to the Research Ethics Board and Health Canada as per the University of Saskatchewan Serious Adverse Events Reporting Policy and the Health Canada Guidance for Clinical Trial Sponsors document. Any serious unexpected adverse drug events will be reported to Health Canada. During the course of the trial, the sponsor will inform Health Canada of any serious unexpected adverse drug reaction (SUARD) as follows:

- o (a) if it is neither fatal nor life threatening, within 15 days after becoming aware of the information; and
- o (b) if it is fatal or life threatening, within seven days after becoming aware of the information.

Definitions of reactions are as follows:

Serious Adverse Drug Reaction: An adverse drug reaction that requires in-patient hospitalization or prolongation of existing hospitalization, that causes congenital malformation, that results in persistent or significant disability or incapacity, that is life threatening or that results in death.

Serious Unexpected Adverse Drug Reaction (SUADR): A serious adverse drug reaction that is not identified in nature, severity or frequency in the risk information set out in the investigator's brochure or on the label of the drug.

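### The protocol breaks the blind through the principal investigator for any adverse event, which conflicts with its own statement that study investigators are blinded and may collect outcome data

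*Protocol*

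**What the plan says.** Trial Design in the protocol lists who is blinded: "Group allocation will be blinded to study participants, study investigators, post-anesthetic care unit (PACU) nursing staff, and surgical ward nursing staff". The principal investigator is not excepted. The attending surgeon and anesthesiologist on the day are the only roles named as unblinded. On who gathers the data, the same section says: "A blinded, centralized, third-party research assistant or study investigators will carry out data collection".

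Selection and withdrawal of subjects states: "All adverse events and protocol deviations will be reported to the study coordinator, study investigators, and appropriate Research Ethics Board". A patient withdrawn because of an adverse event "will be followed up by one of the study's physician investigators while in hospital". The paragraph closes with the rule at issue: "Any adverse events will result in unblinding by notification of the principle investigator".

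Assessment of safety adds: "Adverse events will be recorded in the data collection tool". It defines serious adverse drug reactions and serious unexpected ones, but ties the breaking of the blind to neither.

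**The concern.** A protocol normally keeps the investigator masked when an adverse event is reported and opens the code only when someone has to know the arm. This one makes unblinding the automatic consequence of any event, although elsewhere it counts investigators among the blinded and lets them collect outcomes.

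At stake are the judgements about a patient that follow the unblinding: whether the event was related to the study drug, what later examinations of the injection sites show, and what is taken from the chart. Each involves some discretion, and knowing the arm could influence it.

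**Working it through.** The protocol gives no figure to reproduce, so the check is a comparison of its provisions.

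1. **Trigger.** The rule in Selection and withdrawal of subjects covers any adverse event. No section narrows it by severity, seriousness, relatedness or clinical need. Assessment of safety contains two definitions that could have served as a threshold, but does not link them to unblinding.

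2. **Who learns the allocation.** The sentence names only the principal investigator. It can mean that this person is told the arm, or that notifying this person sets off the code break. On either reading a break of the blind follows every adverse event, and the protocol does not say who else learns the result.

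3. **Who is meant to be blinded.** Trial Design includes study investigators without exception. The single-blinded label in the same section does not settle the matter, because the explicit list goes further than the label.

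4. **What an unblinded investigator may still do.** Trial Design allows investigators to collect data. Selection and withdrawal of subjects has a physician investigator follow patients withdrawn for an adverse event, and provides for a note in the medical record if the event is believed to be drug-related. Assessment of safety requires injection-site examinations daily and at six weeks without naming the examiner. No provision removes a person from these tasks once that person knows the arm.

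5. **What the rule can and cannot reach.**
   - Opioid totals from the pump are logged automatically, so there is little room for influence. The chart-review part of the opioid total is more open.
   - The finding that triggers the unblinding is made before the arm is known. Only later judgements on that patient are exposed.
   - An event first seen at the six-week visit cannot alter a 48-hour opioid total already recorded.

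6. **Number of patients.** The protocol states no adverse event rate. The following is illustration only, with assumed proportions of the 120 planned patients having at least one event:
   - 10%: 0.10 × 120 = 12
   - 30%: 0.30 × 120 = 36
   - 60%: 0.60 × 120 = 72

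   The range is too wide to say whether few or most patients would be affected.

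**The case against.** The strongest reply is that the sentence is loose drafting and reaches little. It closes a paragraph on withdrawal, directly after provisions on patients withdrawn for adverse events, and may have been meant only to describe how a code break is requested. It names one role. The protocol also offers a blinded research assistant as data collector, and the primary outcome is largely machine-recorded.

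Much of this stands, and it limits the point. It does not remove the conflict: whatever was intended, the text makes unblinding the result of any event, and a reader following it would break the blind without need.

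Several stronger readings are tempting but not supported:

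- **That blinding of the trial is defeated, or that investigators generally are unblinded.** Other investigators receive adverse event reports, but nothing says they receive the allocation. Under the text, patients and nursing staff stay blinded.
- **That a large share of patients is affected.** No rate is given, and adverse events that are not serious are not defined.
- **That unblinding will occur more often in one arm because dexamethasone reduces nausea.** The Background Information bases this on injection into caesarean incisions, compared with placebo. It does not concern this block or this surgery, and nothing says ordinary nausea would be counted as an adverse event.
- **That exclusion decisions would be biased.** The final say lies with the attending surgeon or anesthesiologist, who already know the arm, and exclusion after rescue dexamethasone follows a fixed rule.
- **That the interim look is compromised.** The principal investigator would see adverse events by arm, not opioid use by arm, and the planned interim analysis of safety parameters by arm needs allocation data in any case. The Stopping Criteria sentence "If any adverse events are identified in either arm, a safety review will be performed" has an equally low trigger but says nothing about breaking the blind.

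**Conclusion.** The point holds as a specific inconsistency. The unblinding rule in Selection and withdrawal of subjects cannot be followed as written while keeping to the blinding list in Trial Design. The principal investigator could learn the arm of each patient with an adverse event and go on to make judgements about that patient.

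The exposure is confined to patients with events, to what happens after the code is broken, and mainly to relatedness, later injection-site checks and chart review. The number of patients cannot be derived from the protocol. The effect on the pump-recorded opioid total is likely small. The conclusion assumes only that the word any carries its plain meaning, since no other section qualifies it. The change should be made: the rule breaks the blind without need, and correcting it is cheap.

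**What to change.** Reconcile the two sections as follows:

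- Report every adverse event to the principal investigator with the allocation masked.
- Break the code only when the allocation is needed for the patient's care or for expedited regulatory reporting.
- Route code breaks through a named allocation holder who does not collect outcome data. This needs stating, because Trial Design describes both the person who conceals the allocation and the blinded data collector as a centralized third-party research assistant.
- Log each code break with its date, its reason and who learned the allocation.
- Bar anyone unblinded for a patient from collecting or adjudicating that patient's remaining outcome data.

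Reporting to the ethics board and Health Canada continues unchanged. The cost is a protocol amendment, a code-break log and a clear separation of two roles. The downside is that relatedness of minor events is judged without knowing the arm.
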